Statistical Analysis Plan

NCT04102228

Repetitive Transcranial Magnetic Stimulation and Multi-modality Aphasia Therapy for Post-stroke Non-fluent Aphasia (REMAP)

Finalized September 25, 2023.

Uploaded to Clinicaltrials.gov on October 5, 2023, after completion of data collection and prior to outcome data analysis.

Sample Size Determination

The trial will consist of two parallel cohorts (sub-acute and chronic stroke) with identical study interventions and procedures. The sample size is based upon a minimal clinical important difference of 5 points on the Western Aphasia Battery, a standard deviation of 15 and a correlation between pre- and post- measurements of 0.9. These estimates are concordant with the psychometric properties of the Western Aphasia Battery. Therefore, with 23 patients per intervention or sham group and therefore 46 patients in each cohort (N=92 in total), the study will have 85% power within each cohort (sub-acute and chronic). The sample will be inflated to 100 to account for any loss to follow-up.

General statistical methods

Data related to baseline measures and participant demographics will be compared between groups using t-tests or Fisher's exact tests. If a baseline factor is found to differ between groups, it will be considered for inclusion as a covariate during hypothesis testing. Our primary analysis will follow intent-to-treat methods and any missing data will be handled with the restricted maximum likelihood method, assuming that data are missing at random. We will first assess for heterogeneity of treatment effect with all patients (n=100) and include stroke cohort (sub-acute and chronic) and a treatment-by-cohort interaction term. If there is evidence of heterogeneity, we will present a cohort-specific analysis assessing for treatment effect.

Hypothesis testing

To test our primary hypothesis that compared with 10 days of sham stimulation and multi-modality aphasia therapy, 10 days of 1Hz rTMS combined with multi-modality aphasia therapy will elicit significantly greater improvement in Western Aphasia Battery Aphasia Quotient scores, we will use a linear mixed-effects model. In this model, we will use fixed effects for group (rTMS, Sham), time (Pre-treatment, Post-treatment, 3-months), a group by time interaction, baseline WAB AQ scores, age at intervention and sex, with an unstructured covariance matrix.

Secondary outcomes will be tested separately using the same model. The Benjamini-Hochberg procedure will be used to account for multiple comparisons among secondary outcomes, which include trained and untrained nouns and verbs, the scenario test, the communication effectiveness index, Stroke Aphasic Depression Questionnaire, Stroke and Aphasia Quality of Life scale, and measures of descriptive discourse (number of words per minute and correct information units per minute during connected speech samples).

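### The pooled primary model lists neither cohort nor cohort-by-time, so any difference in recovery between the two cohorts widens its confidence interval

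*SAP*

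**What the plan says.** Cohort is a design factor. Sample Size Determination opens: "The trial will consist of two parallel cohorts (sub-acute and chronic stroke) with identical study interventions and procedures". Each cohort is sized separately, "with 23 patients per intervention or sham group and therefore 46 patients in each cohort (N=92 in total"), on the basis of "a standard deviation of 15 and a correlation between pre- and post- measurements of 0.9".

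General statistical methods describes a first step on all patients that will "include stroke cohort (sub-acute and chronic) and a treatment-by-cohort interaction term". One consequence is written: "If there is evidence of heterogeneity, we will present a cohort-specific analysis assessing for treatment effect". Nothing is written for the case where heterogeneity is not found. The only other route for a covariate is a data-driven one: "If a baseline factor is found to differ between groups, it will be considered for inclusion as a covariate during hypothesis testing".

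Hypothesis testing then gives the primary model: a linear mixed model with "fixed effects for group (rTMS, Sham), time (Pre-treatment, Post-treatment, 3-months), a group by time interaction, baseline WAB AQ scores, age at intervention and sex", and an unstructured covariance. The same model is carried over to every secondary outcome.

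The opening lines date the SAP's posting to a point "after completion of data collection and prior to outcome data analysis".

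**The concern.** Sub-acute and chronic patients may well differ in how much they recover over the study, whatever their arm. A pooled model that cannot represent such a difference puts it into the residual variance of change. The treatment estimate stays unbiased, but its interval is wider than the design requires and power is lost.

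No rule in the SAP reliably brings the needed term in:

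- The heterogeneity step names cohort and treatment-by-cohort, but not cohort-by-time, and does not say that either named term is kept after a negative result.
- The baseline-difference rule acts only on factors that differ between arms. Cohort will not differ if arms are balanced within cohort. Even when triggered, the rule only considers a covariate and mentions no time interaction.

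The two sections do not contradict each other. The gap is the unwritten content of the pooled fit after a negative heterogeneity step.

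**Working it through.** **Inputs.** From the SAP: difference 5 WAB points, SD 15, pre-post correlation 0.9, 23 per arm per cohort, hence 46 per arm pooled (N = 92). Not in the SAP and therefore assumed: two-sided 5% level; difference in mean recovery between cohorts, D, from 0 to 10 points. The SD is read as a within-cohort figure because power is stated within each cohort.

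**The plan's own figure (85% per cohort, 23 per arm).** Power = Φ(5/(SD·√(2/23)) − 1.96).

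- Change score, SD = √(2·225·(1 − 0.9)) = √45 = 6.71: 71.5%.
- ANCOVA at one post-treatment visit, SD 6.54: 73.7%.
- ANCOVA on the mean of two post-treatment visits, SD = 15·√(0.95 − 0.81) = 5.61: 85.6%. This also needs a correlation of 0.9 between the two post visits, which the SAP does not state.

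The stated 85% is matched by the last of these. That is a separate matter. The main calculation below uses the change variance of 45, because change is what the listed model's group-by-time contrast estimates; the other two serve as sensitivity checks.

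**Why a cohort main effect is not enough.** With pre-treatment as a level of time and complete data, a covariate without a time interaction shifts all visits equally and cancels from change. This holds for baseline AQ, age, sex and a cohort main effect. The group-by-time contrast is then the plain difference in mean change. A REML fit of the three-visit model to simulated data (N = 92, unstructured covariance, all correlations 0.9, baseline AQ as a separate reading) confirmed this. The estimate equalled the difference in mean change to within 2e-12, and adding a cohort main effect left the standard error unchanged (ratio 1.0000 at every D).

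**Effect of omitting cohort-by-time.** If a share p of patients is in one cohort, the variance of change rises by p(1 − p)D², which is D²/4 for equal cohorts.

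- Interval ratio = √((45 + D²/4)/45).
- Patient equivalent = 92·(D²/4)/(45 + D²/4).
- SE_true = √(2·45/46) = 1.399; SE_model = √(2·(45 + D²/4)/46).
- Power with the terms = Φ(5/SE_true − 1.96) = 94.7%.
- Power without them = Φ((5 − 1.96·SE_model)/SE_true) if arms are balanced within cohort, or Φ(5/SE_model − 1.96) if not.
- Type I error if balanced = 2·(1 − Φ(1.96·SE_model/SE_true)).

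| D | Extra interval width | Half-width (AQ points) | Patients' worth of precision lost | Power, balanced / not | Type I error, balanced |
|---|---|---|---|---|---|
| 0 | 0% | 2.74 | 0 | 94.7% / 94.7% | 5% |
| 2 | 1.1% | 2.77 | 2.0 | 94.4% / 94.2% | not computed |
| 5 | 6.7% | 2.93 | 11.2 | 93.1% / 91.8% | 3.6% |
| 10 | 24.7% | 3.42 | 32.9 | 87.1% / 81.8% | 1.5% |

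Solving for D, √(180·(w² − 1)) gives a 5% wider interval at D = 4.3 and a 10% wider one at D = 6.1. Without balance within cohort, the type I error stays near 5%.

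**Simulation of the contrast (t-based, N = 92, 20,000 runs per cell), without versus with cohort-by-time.**

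- Balanced, D = 5: type I error 3.7% vs 5.0%, power 92.4% vs 94.3%.
- Balanced, D = 10: type I error 1.6% vs 5.2%, power 86.4% vs 94.5%.
- Not balanced, D = 5: type I error 4.8% vs 4.8%, power 91.3% vs 94.0%.
- Not balanced, D = 10: type I error 4.8% vs 4.7%, power 81.1% vs 94.1%.

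**Sensitivity to the variance.** At D = 2, 5 and 10 the excess width is 1.2%, 7.1% and 26% with single-visit ANCOVA, and 1.6%, 9.5% and 34% with the mean of two post visits.

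**Price of the terms at D = 0.** Nothing if arms are balanced within cohort. If not, about 0.6% of interval width on average and about 2% at the 95th percentile of allocations.

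**The case against.** The strongest reply is that cohort is already in the plan. The all-patient step includes it, and no sentence removes it. In a model whose treatment effect is group-by-time, treatment-by-cohort can be read as a three-way term, which by the usual hierarchy would bring cohort-by-time with it. That reading is possible, but the explicit list under Hypothesis testing does not say it, and a primary model should not depend on it.

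Several qualifications stand:

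- The size rests on D, which the SAP does not supply. At D = 2 the cost is negligible, and D = 10 is twice the plan's own important difference. By the formulas above, pooled power stays at 85% or more until D is about 8.7 (not balanced) or 11.0 (balanced).
- D²/4 is the maximum, reached with equal cohorts. Achieved cohort sizes are not in the SAP.
- Exact cancellation of the main effect needs complete data and pre-treatment as a response. If only post-treatment visits are responses, a cohort main effect would absorb a difference common to both visits.
- Treating baseline AQ as a separate reading was a device of the REML check; the SAP does not describe one.
- The variance of 45 does not reproduce the stated 85%, so the power figures should not be read to the decimal.

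None of this restores the missing terms. It limits the weight of the point.

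**Conclusion.** The point holds, as a modest and nearly free improvement rather than an error that threatens the conclusion. The listed pooled model contains neither cohort nor cohort-by-time, and the branch after a negative heterogeneity step is unwritten.

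The loss is one of precision: roughly 1% of interval width at D = 2, 7% to 10% at D = 5 and 25% to 34% at D = 10, depending on the variance taken. There is no bias. The test is conservative if arms are balanced within cohort; the planned 23 per arm per cohort implies that balance, but the SAP does not state it as a randomisation rule. Otherwise the test keeps its level and is less precise. Cohort-specific fits are unaffected.

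The figures assume a within-cohort SD of 15, correlation 0.9, equal cohorts, complete data, a two-sided 5% level and the stated range of D.

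**What to change.** Add cohort and cohort-by-time as fixed effects to the pooled primary model, state that they are kept whatever the heterogeneity step shows, and do the same for the secondary outcomes fitted with that model. If only post-treatment visits are used as responses, add cohort and cohort-by-visit instead.

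With three time levels this is three extra parameters (one for cohort, two for the interaction). Cohort is known for every patient, so no new data are needed. The statistical price is the small one shown above at D = 0.

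Make the change by dated amendment before outcome data are analysed. The SAP places itself before that analysis, but whether analysis has since begun cannot be told from the document. If it has, the cohort-adjusted fit should be reported as a labelled sensitivity analysis.

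### The primary mixed model uses baseline WAB AQ both as a response and as a covariate, so with an unstructured covariance REML has no solution and the stated adjustment drops out

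*SAP*

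**What the plan says.** Under Hypothesis testing, the SAP specifies a linear mixed-effects model for WAB AQ. The fixed effects include "time (Pre-treatment, Post-treatment, 3-months"), so the pre-treatment score is a response. The same sentence then adds "a group by time interaction, baseline WAB AQ scores, age at intervention and sex, with an unstructured covariance matrix". The hypothesis is stated as "significantly greater improvement in Western Aphasia Battery Aphasia Quotient scores", which points to the group-by-time interaction as the contrast of interest.

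General statistical methods names the estimation method: "any missing data will be handled with the restricted maximum likelihood method, assuming that data are missing at random". For the secondary outcomes the SAP says "Secondary outcomes will be tested separately using the same model".

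The SAP does not remove the pre-treatment row from the response, give baseline its own slope at each time, constrain the groups to be equal at pre-treatment, or define baseline as an assessment distinct from pre-treatment.

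**The concern.** A measurement can be conditioned on as a covariate or modelled as a response. Here it is both. In every pre-treatment row the response equals the covariate, so nothing is left to estimate at that visit, yet the unstructured matrix assigns the visit its own variance and covariances.

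Two things are at stake. First, software will fail to converge, report a covariance matrix that is not positive definite, or stop at an arbitrary boundary. The analyst must then choose another model with outcome data open. The SAP was finalised after data collection and before outcome analysis, so fixing the primary model in advance is much of its purpose. Second, any fit that is obtained will be read as adjusted for baseline, age and sex, when the treatment-by-time contrast is not adjusted in the way the plan states.

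**Working it through.** **Inputs from the SAP.** Three response times, covariates and unstructured covariance (Hypothesis testing); REML (General statistical methods); difference 5, SD 15, pre-post correlation 0.9, 23 per arm in each cohort, 85% power (Sample Size Determination).

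**Assumptions.** Baseline AQ is the pre-treatment AQ. The unstructured matrix is the 3×3 within-patient covariance. Two-sided alpha is 0.05, and the two follow-ups also correlate 0.9; the SAP states neither.

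**The plan's power figure.** A baseline-adjusted comparison of the mean of two follow-ups has SD 15 × √((1 + 0.9)/2 − 0.81) = 15 × √0.14 = 5.61. With 23 per arm and a difference of 5, power is 85.6%, which reproduces the stated 85%.

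**Why the likelihood has no maximum.** For patient i at pre-treatment the model is

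B_i = intercept + group + β·B_i + age + sex + e_i.

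With β = 1 and the other terms 0, every e_i is exactly 0. Let the pre-treatment residual SD σ₀ shrink. Then −2 log REML behaves as (N − 5)·log σ₀², where 5 is the number of coefficients in that row. Each tenfold fall in σ₀ should lower it by (N − 5) × 2 × ln 10:

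- N = 46: 41 × 4.605 = 188.8
- N = 100: 95 × 4.605 = 437.5

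Simulated data with SD 15 and all correlations 0.9, fitted with the fixed effects as written:

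| σ₀ | −2 log REML, N = 46 | −2 log REML, N = 100 | Baseline slope, N = 46 | Age, N = 46 | Group × post, N = 46 | SE |
|---|---|---|---|---|---|---|
| 10 | 627.46 | 1392.28 | 0.875 | 1.783 | 3.689 | 3.551 |
| 1 | 441.71 | 961.06 | 0.995 | 0.065 | 3.689 | 2.001 |
| 0.1 | 253.08 | 523.85 | 1.000 | 0.001 | 3.689 | 1.979 |
| 0.01 | 64.27 | 86.36 | 1.000 | 0.000 | 3.689 | 1.979 |
| 0.0001 | −313.35 | −788.62 | 1.000 | 0.000 | 3.689 | 1.979 |

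From 0.1 to 0.01 the falls are 188.81 and 437.49, as predicted. An unrestricted optimiser ran to the lower bound set on σ₀ in both data sets.

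**What remains of the adjustment.** Subtract the pre-treatment row from a follow-up row. Baseline, age and sex have the same value and coefficient in both, so they cancel and only time and group remain. The interaction is then the raw difference in change:

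| Data set | Model as written (post, 3 months) | Raw change difference | Baseline-adjusted analysis |
|---|---|---|---|
| N = 46 | 3.689, 3.143 | 3.689, 3.143 | 4.637, 4.059 |
| N = 100 | 5.564, 3.526 | 5.564, 3.526 | 5.589, 3.840 |

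In the limit the SE also equals that of the change score (1.979 at N = 46; 1.462 at N = 100, for the post-treatment visit). With complete data the point estimate equalled the raw change difference for every covariance matrix tried.

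**Cost in precision.** Change-score variance is 225 × 2(1 − r); baseline-adjusted variance is 225 × (1 − r²). At r = 0.9 these are 45 and 42.75, a ratio of 1.053. At r = 0.8 and 0.7, which are not in the SAP and are shown only as a range, the ratios are 0.40/0.36 = 1.11 and 0.60/0.51 = 1.18. A 4,000-run simulation with age and sex as noise covariates gave penalties of 2%, 7% and 16%.

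Power at 23 per arm, adjusted against change score: 73.7% and 71.5% for one follow-up; 85.6% and 83.1% for the mean of two. For 85% power on the mean of two, 23 and 25 per arm are needed.

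**The case against.** The strongest reply is that the SAP does not say which matrix is unstructured. If it means the random-effects matrix with a common residual variance, REML can converge: a random-intercept fit to the N = 46 data gave −2 log REML 590 and a baseline slope of 0.89. That stands, so the claim that the model cannot be fitted depends on the residual-covariance reading. It does not rescue the adjustment, because in that fit the group-by-time estimate was still 3.689, the raw change difference. Some adjustment would enter a group contrast taken at the post-treatment visit (0.62 + 3.69 = 4.31), but a hypothesis about improvement points to the interaction. With about 8% random dropout the cancellation is no longer exact, and random-intercept estimates moved by only 0.01 to 0.08 points.

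Other points also stand:

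- A change-score comparison is unbiased under randomisation and does subtract baseline. What is lost is the estimated baseline slope and the age and sex adjustment, not validity.
- At r = 0.9 the efficiency loss is small and would not by itself make the correction essential.
- If baseline were a separate assessment, the exact singularity would not arise. The SAP names no such assessment.
- For secondary outcomes the singularity recurs only if each outcome's own baseline is used. If WAB AQ is carried over literally there is no singularity, but with complete data the covariate still cancels from the interaction.

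**Conclusion.** The concern holds. Read plainly, the primary model has an unbounded REML likelihood, and its limiting treatment estimate is an unadjusted change-score difference. Under the alternative random-effects reading it converges, but the group-by-time contrast still lacks the stated adjustment when data are complete. These conclusions take baseline AQ to be the pre-treatment AQ and the group-by-time contrast to be the primary test.

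The average efficiency cost is modest: 5% in variance at r = 0.9, or about 2 to 2.5 points of power. The reason to correct it is that the primary test is not fixed in advance. Plausible repairs give different answers on the same data (3.69 or 4.64 in the 46-patient example), and the choice would be made with outcomes in view.

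**What to change.** Amend the model sentence, with a date, before outcome data are analysed, so that baseline appears once.

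- **Preferred form:** responses are the post-treatment and 3-month scores only. Fixed effects are group, time, group-by-time, baseline AQ, baseline-by-time, age and sex, with an unstructured 2×2 within-patient covariance.
- **Alternative form:** keep all three times as responses, drop the baseline covariate, constrain the group means to be equal at pre-treatment, and let age and sex interact with time, with an unstructured 3×3 covariance.

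The preferred form leaves out patients with no follow-up score. The alternative keeps them, and suits the SAP's intent-to-treat statement better if every randomised patient is meant to be in the model. Either way, say explicitly that the unstructured matrix is the within-patient residual covariance. For each secondary outcome, state that its own baseline is used in the same way.

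The cost is one corrected sentence and a changed model statement. No new data are needed.

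### The primary model leaves out time from stroke to start of treatment, a cheap pre-specified covariate that could buy precision, mainly in the sub-acute cohort

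*SAP*

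**What the plan says.** The design rests on stroke phase. Sample Size Determination states: "The trial will consist of two parallel cohorts (sub-acute and chronic stroke) with identical study interventions and procedures". It sizes each cohort separately, at 23 per arm and 46 per cohort.

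Hypothesis testing gives the primary model's fixed effects as group, time (one visit before treatment and two after), their interaction, and "baseline WAB AQ scores, age at intervention and sex, with an unstructured covariance matrix". Neither time from stroke nor stroke cohort is listed there.

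Two provisions under General statistical methods bear on the point:

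- A first step on all patients will "include stroke cohort (sub-acute and chronic) and a treatment-by-cohort interaction term". After that: "If there is evidence of heterogeneity, we will present a cohort-specific analysis assessing for treatment effect".
- For other baseline variables: "If a baseline factor is found to differ between groups, it will be considered for inclusion as a covariate during hypothesis testing".

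The SAP gives no time window for either cohort, no spread of onset times, and no figure for spontaneous recovery.

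**The concern.** If recovery is still under way in the sub-acute cohort, change after treatment depends partly on how long after the stroke the participant started. None of the listed covariates carries that information. It then stays in the residual and widens the interval for the rTMS effect.

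The existing provisions help only in part:

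- **Cohort term.** It absorbs the sub-acute versus chronic difference. It is constant within the sub-acute cohort, and it drops out of a cohort-specific analysis.
- **Baseline rule.** It acts only when a factor differs between arms, and then it obliges no one. Under randomisation a 5% test fires in about 5% of trials, however prognostic the factor is. With 23 per arm it needs an imbalance of about 2.015 × √(2/23) = 0.59 SD. Whether a covariate improves precision depends on its link with outcome, not on that test.

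What is at stake is the width of the interval in a small trial, chiefly in the 46-patient sub-acute comparison.

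**Working it through.** **Inputs from the SAP (Sample Size Determination):** "minimal clinical important difference of 5 points on the Western Aphasia Battery"; SD 15; pre-post correlation 0.9; 23 per arm per cohort; stated power 85% within each cohort. The SAP states neither alpha nor sidedness, so two-sided 0.05 is assumed.

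**Input not in the SAP:** the correlation r between time from stroke and gain (the outcome after adjustment for baseline) in the sub-acute cohort. It is assumed to be 0.2, 0.3 or 0.5, with 0 as the case of no value.

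**1. The plan's own power.** Power = Φ(5/SE − 1.96), with SE = s × √(2/23).

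| Analysis | s | Power |
|---|---|---|
| Change score | 15√(2 × 0.1) = 6.71 | 71.5% |
| Baseline-adjusted, one post-treatment visit | 15√(1 − 0.81) = 6.54 | 73.7% |
| Baseline-adjusted, mean of two post-treatment visits, all correlations 0.9 | 15√(0.95 − 0.81) = 5.61 | 85.6% |

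The stated 85% is reproduced on the third reading. The steps below use the second (SE 6.54 × 0.295 = 1.93); the proportional savings do not depend on that choice.

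**2. Sub-acute cohort, 23 per arm.** Adjustment multiplies the SE by √(1 − r²). Estimating one more slope costs about 1/(2 × residual df), here 1/(2 × 42) = 1.2%.

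| r | √(1 − r²) | × 1.012 | SE saved | SE | Power, one visit |
|---|---|---|---|---|---|
| 0 | 1.000 | 1.012 | −1.2% | 1.95 | 73% |
| 0.2 | 0.980 | 0.992 | 0.8% | 1.91 | 74% |
| 0.3 | 0.954 | 0.965 | 3.5% | 1.86 | 77% |
| 0.5 | 0.866 | 0.876 | 12.4% | 1.69 | 84% |

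Simulation with baseline adjustment agrees: the SE falls from about 1.94 to 1.92, 1.87 and 1.70 at r = 0.2, 0.3 and 0.5, and rises about 1% at r = 0.

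**3. Pooled analysis, 92 patients, cohort term already in the model.** Suppose time from stroke matters only in the sub-acute half. A slope fitted there removes r²/2 of the residual variance, at a cost of 1/(2 × 87) = 0.57%.

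- r = 0.2: √0.980 × 1.0057 = 0.996, about 0.5% saved
- r = 0.3: √0.955 × 1.0057 = 0.983, about 2% saved
- r = 0.5: √0.875 × 1.0057 = 0.941, about 6% saved

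One slope shared by both cohorts would remove only r²/4: about 0%, 0.6% and 2.6%. Free slopes in both cohorts cost 2 × 0.57 = 1.1%, leaving about 0%, 1.2% and 5.4%.

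**4. Bias and test size.** In 20,000 simulated trials per setting, with time from stroke explaining 10% to 40% of residual variance and left out of the model, the mean error was within 0.01 points of zero. Type I error was 4.7% to 5.2%.

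**5. Why a by-visit term is needed.** The pre-treatment score is one of the model's outcome visits. A covariate entered only as a main effect adds the same amount at every visit, so with complete data it cancels from post minus pre and leaves the group-by-time contrast unchanged. Only a covariate-by-visit term acts on change.

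**The case against.** The strongest case against is that this is a preference. The SAP already pre-specifies three covariates, puts cohort in a first step, and has a rule for baseline differences. Omitting one more prognostic variable contradicts nothing in it. A narrow sub-acute window, which the protocol may set, would leave little to adjust for. The pooled analysis comes first, and there the gain is small.

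Most of this stands, and it limits the point to an inexpensive improvement. What survives is that this variable is tied to the trial's own cohort definition, that the trial must have dated each stroke well enough to assign a cohort, and that the fallback rule selects covariates by a test unrelated to their value.

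A reader might infer that the omission biases the rTMS effect, because a chance imbalance in time from stroke shifts the estimate. The documents do not support that. In a randomised comparison such a shift is sampling variation already counted in the standard error, as step 4 shows. Nor is it a second harm beside the wider interval. At r = 0.3 its SD is 0.3 × 6.71 × √(2/23) = 0.59 points. Removing about 0.60 from an unadjusted change-score SE of about 1.97 gives √(1.97² − 0.60²) = 1.88, close to the simulated adjusted value of 1.90.

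**Conclusion.** The point holds as one of efficiency. The primary model omits a plausible prognostic baseline value, and the cohort term and the baseline rule cover it only partly. The analysis as written is valid: no systematic bias, and a test of correct size.

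The size rests wholly on the assumed correlation. The saving in the sub-acute comparison runs from about 1% to 12 to 13% of the SE over r = 0.2 to 0.5. In the pooled analysis it is about 0.5% to 6%, provided the slope is fitted where it matters. The upper figures belong to r = 0.5 only. At r = 0.2 the gain is marginal, and at 0 there is a loss of about 1%. Any overlap of time from stroke with baseline WAB AQ, age or sex would shrink the gain further; that overlap was not explored. A reading that the rTMS estimate is untrustworthy without this covariate goes beyond what the SAP shows.

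**What to change.** In Hypothesis testing, add stroke cohort and time from stroke onset to randomisation to the pre-specified covariates of the primary model. Enter time from stroke as, for example, log days centred within cohort, and let its slope differ by cohort. Give each a by-visit term so that it acts on change from the pre-treatment visit. Keep time from stroke in any cohort-specific analysis. State that both are included whatever the baseline comparisons show.

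The cost is a sentence or two in the SAP, with no new visits or patients. It uses a few degrees of freedom and widens the interval by about 1% if time from stroke is not prognostic. The change belongs before outcome analysis, the stage at which the SAP says it was uploaded. If results by arm have already been seen, report the adjusted model as a sensitivity analysis instead.
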